### Theme 1: Applying rTMS treatment and its evaluation by neuropsychological and clinical assessments

1. Recruit people (from Riverview Health Center and also from [name] referrals), who have had a head injury within the past two to 12 months, have a clear diagnosis of TBI, and have persistent post-TBI symptoms. Collect standard neuropsychological assessment data at baseline.

2. Enroll the study participants into a “Sham Group” and a “Treatment Group” with a three-week protocol, and apply the treatment.
3. Record spatio-temporal assessments before and after treatment sessions, and examine the efficacy of rTMS treatment on the post-TBI symptoms by standard clinical and neuropsychological assessments by statistical analysis.

Theme 2: Monitoring treatment efficacy by objective measures, EVestG and spatio-temporal assessments

4. Record EVestG data with all its seven current stimuli at baseline (before the treatment) and immediately after treatment and also four and eight weeks after the last treatment.
5. Analyze EVestG data for extracting the optimum measures (biofeatures) showing the changes due to rTMS treatment.
6. Optimize (reduce the number of stimuli if possible) the EVestG recording protocol upon the results of Objective 5.
7. Examine the statistical correlation of the EVestG biofeatures representing the TBI recovery with data from the clinical and neuropsychological assessments as well as spatio-temporal assessments (derived in Objective 3).

Theme 3: Evaluating the objective measures of EVestG and spatio-temporal assessments in Control group

8. Recruit 20 age-and-gender-matched individuals with no history of head injury and record their EVestG data four times with a similar schedule to that of TBI patients, and investigate the consistency of the EVestG data between the sessions and compare with those of people with TBI during treatment.
9. Run the spatio-temporal assessments at the same sessions of EVestG recording in the Control Group and examine the effect of learning on the performance in these assessments.

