### **Study Protocol**

#### **Study Population/Participants**

A total of 20 individuals with a clear diagnosis of TBI within the last 12 months (as confirmed by their treating Neurologist, Psychiatrist or Medical Rehab Physiatrist, who are the co-investigators in this study) prior to the commencement of this study will be recruited from Riverview Health Center patient and [name] clinic patient population. Ten patients will be randomly assigned to **Treatment Group** and 10 others to **Sham Group**. Neither the patients, nor the clinical assessors will know the sham versus real treatment group assignment. In addition, as one of the objectives of this study is to evaluate the EVestG assessment as a

diagnostic and monitoring tool, 20 age-and-gender-matched cognitively healthy volunteers will be recruited as controls for the EVestG assessment. The healthy **Control Group**'s participants must not have any history of TBI and also meet other exclusion criteria for patients group listed below.

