### **EVestG Measurement**

All study participants (in all three groups) will go through four sessions of EVestG assessments: 1) before rTMS treatment, 2) after 12 sessions of rTMS treatment, 3) four weeks after the last rTMS treatment, and 4) eight weeks after the last rTMS treatment.

The subjects sit in a hydraulic chair with their eyes closed and head rested on the chair headrest; they receive a series of orthogonal passive whole body movement stimuli: up/down translation and a horizontal rotation to the right and return to center (RTC) in both sitting upright and supine positions, and side tilts to the right and left.

Each tilt and the rotation are about 40 degrees, while up/down movement are about eight inches; the movements are designed to be smooth with a constant acceleration/deceleration over 3s. The recordings are made in an acoustically attenuated (>30dB) and electromagnetically shielded chamber at the EVestG Lab, Riverview Health Center. The active gelled recording electrodes are TM-EcochGtrode (Bio-logic, France), and placed in both ears proximal to the eardrum. Reference electrodes (Biopac EL254S for earlobe and EL258S for forehead) are placed on the ipsilateral earlobes and a common ground electrode is placed on the forehead.

The left and right ears' signals are recorded using Spike2 software via a CED-1902 amplifier (60Hz notch filter, 10k gain, 1Hz high pass filter) and digitized using CED1401 ADC board at sampling rate of 41,666Hz. Each recording's duration was 60s for each stimulus: 20s stationary at the center position, 3s motion to a position (up or rotated), 17s stationary in that position, 3s return to the center, and another 17s of stationary recording in the center position.

The chair's position is also recorded simultaneously with the ear signals; it is used to extract the segments of interest for analysis. The particular segments of interest, shown in Figure 2, are: 1.5s immediately prior to the movement (BGi), 1.5s acceleration (onAA) and 1.5s deceleration (onBB) as well as the 1.5s segments from the return to the center: RTC BGi, RTC onAA and RTC

onBB. The acceleration/deceleration segments are selected as they give the largest differences compared to background. Each EVestG recording may take up to one hour.

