### **Data analysis**

**EVestG Biofeature Extraction** – The NEER algorithm [52] will be used to locate and extract vestibular neural events. The interval histograms of the neural events are also used to extract the basic statistical properties of the neural firings such as probability density function (pdf), mean and variance, as well as fractal dimension, kurtosis and skewness of the signal. The features extracted from all tilts will be investigated to determine biofeatures specific to a concussion. The extracted biofeatures, e.g. fractal dimension, kurtosis and skewness of the potentials' distribution, from the recorded signal will be compared between Sham and Treatment Groups.

[figure not shown]
**Statistical Analysis, Clustering, Decision Making and Validation** – After data collection, the multivariate Analysis of Variance (MANOVA) statistical test will be run to determine the significant differences of any of the extracted biofeature measures between the sessions and the Control Group and the Treatment and Sham Groups. In all instances, a p-value less than 0.05 is considered significant. Cross correlation analysis will also be used to find the correlation between these measures and the neuropsychological assessments scores. Once the statistically significant features among the groups are found, the classic approach of discriminant analysis with leave-one-out routine (for robust results in small size data) will be run to investigate whether concussion cases can be identified. An important issue to address is the membership assignment of the subjects. Since there may not be confirmed and solid clinical and neuropsychological assessments for the recovery from the TBI post-symptoms, we will also run unsupervised (blind) clustering of the objective measures followed by our recently developed diagnostic decision making algorithm to identify TBI recovery. The diagnostic and monitoring algorithms will be checked with the updated diagnoses of the clinical symptoms (by the referring physician) and the neuropsychological evaluations.

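### The EVestG comparison across four sessions is a MANOVA with no layout and no missed-session rule, so it either drops anyone who misses a session or treats repeat visits as independent

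*Combined protocol and SAP*

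**What the plan says.** - **Test.** Data analysis (Statistical Analysis, Clustering, Decision Making and Validation) names one inferential test for the EVestG features: a "multivariate Analysis of Variance (MANOVA) statistical test will be run to determine the significant differences of any of the extracted biofeature measures". The comparison is "between the sessions and the Control Group and the Treatment and Sham Groups".
- **Threshold.** "In all instances, a p-value less than 0.05 is considered significant".
- **Repeated measures.** Under EVestG Measurement, all three groups "will go through four sessions of EVestG assessments". Table 1 places them at weeks 0, 4, 8 and 12.
- **Recordings per session.** Objective 4 (Theme 2): "Record EVestG data with all its seven current stimuli at baseline", and again at the three later sessions.
- **Sample.** Study Population/Participants: "A total of 20 individuals with a clear diagnosis of TBI within the last 12 months"; "Ten patients will be randomly assigned to" each of Treatment and Sham. Objective 8 (Theme 3) adds the controls: "Recruit 20 age-and-gender-matched individuals with no history of head injury and record their EVestG data four times".

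The documents do not state how session enters the MANOVA, an analysis set, a rule for missed sessions or unusable recordings, a dropout allowance, a replacement rule, or an imputation method. The analysis paragraph reads continuously, so these are not redactions.

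**The concern.** A MANOVA needs a full response vector for every unit it analyses. When the same person is measured four times, there are two ways to set it up.

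- **Sessions in the vector.** This respects the correlation between a person's visits. A person missing any one session has an incomplete vector and leaves the test, together with the visits that were recorded.
- **Session as a factor, one row per visit.** A missed session costs one row. But the test then counts a person's four visits as four unrelated observations, and its error rates are wrong.

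The plan does not choose, and neither choice is sound once a session is missed. With the first, the EVestG answer comes from people who completed everything. That wastes data and, if those who miss sessions recover or tolerate treatment differently, distorts sham versus active. With the second, group differences are declared too readily. Either way the error carries forward, because features found significant go on to the discriminant analysis.

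**Working it through.** The plan gives no power, effect size, SD or loss rate, so there is no figure of its own to reproduce. From the documents: 4 sessions, 10 v 10 patients, 20 controls, 0.05 threshold (taken as two-sided). Assumed: a loss rate m per session, independent between sessions, and a within-person correlation r.

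**1. Sessions in the vector: who remains**

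P(complete) = (1 − m)^4 if all four sessions are at risk, or (1 − m)^3 if only the three follow-ups are.

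| m | Four at risk | Of 20 | Follow-ups only | Of 20 |
|---|---|---|---|---|
| 2% | 0.922 | 18.4 | 0.941 | 18.8 |
| 5% | 0.815 | 16.3 | 0.857 | 17.1 |
| 10% | 0.656 | 13.1 | 0.729 | 14.6 |
| 15% | 0.522 | 10.4 | 0.614 | 12.3 |

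At 5% to 10% that is 10 × 0.656 = 6.6 to 10 × 0.857 = 8.6 per arm. Even at 2%, the chance that all 20 patients are complete is 0.922^20, about 20%.

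Listwise deletion was checked directly. A four-session MANOVA was fitted to 20 simulated patients, four of whom each lacked one session. It used 16 rows.

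**2. What that costs**

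The standard error of a group difference grows by √(1 / P(complete)): √(1/0.857) = 1.08 to √(1/0.656) = 1.23, so 8% to 23% wider. The standardised difference detectable with 80% power in a simple two-group test is 1.32 at 10 v 10, 1.51 at 8 v 8 and 1.80 at 6 v 6.

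For a two-group Hotelling test with p responses, error df = 2n − p − 1:

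- One feature over four sessions (p = 4): 15 at 10 v 10, 11 at 8 v 8, 7 at 6 v 6.
- Three features over four sessions (p = 12): 7, then 3, then not computable.

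**3. Session as a factor: what happens to the error rate**

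Take one feature. With equal correlation r, the variance of a person's four-visit mean is (1 + 3r) times what independence assumes. The true false-positive rate of the nominal 5% group test is about 2 × [1 − Φ(1.96 / √(1 + 3r))]:

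- r = 0.3: √1.9 = 1.38, giving about 15%.
- r = 0.5: √2.5 = 1.58, giving about 22%.
- r = 0.7: √3.1 = 1.76, giving about 27%.

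Simulation of 10 v 10 with four visits agreed (15%, 22%, 27%). Differences between sessions go the other way: their true variance is (1 − r) times the assumed one, so those tests are too conservative and real change over time is missed.

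**The case against.** The strongest reply is that the plan never says it will analyse complete records only. The wording fits session as a factor with the features as the response vector, and then a missed session loses a row and not a person. This stands. A reader might infer that the plan commits to dropping anyone with a gap, but the documents do not support that, because the layout is unstated. It does not rescue the analysis, since the row-per-visit layout brings the error in step 3.

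The size can also be overstated in three ways.

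- **Counting every signal.** A reader might multiply 7 stimuli × 2 ears × 4 sessions = 56 and conclude that a 1% loss leaves 0.99^56 = 57% of people. That needs 56 values in one vector. With 40 participants in three groups the error df is 40 − 3 = 37, so that MANOVA could not be computed even with complete data. One failed stimulus also need not matter if its features are not used.
- **Crediting the fix with unrecorded visits.** For an assumed 1.2 SD difference, power is 72% at 10 v 10, 54% at 7 v 7 and 47% at 6 v 6. A reader might take that gap as the gain from a mixed model. It is not, because no model recovers a visit that never took place. The fairer contrast is at the last visit with baseline always present, averaging exact power over the binomial number seen per arm. At 5% loss, people complete (0.857 each) give about 64% against 69% for everyone seen at that visit (0.95). At 10% the figures are 55% (0.729) against 66% (0.90).
- **Independent losses.** Withdrawal clusters missed sessions in fewer people, which leaves more complete records for the same overall loss.

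Finally, this is a pilot. That lowers the weight of lost power. It does not justify an analysis with no valid way of handling a missed session.

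**Conclusion.** The point holds in this form: the EVestG comparison across sessions has no stated layout and no rule for missed sessions. Of the two possible layouts, one discards people and the other ignores within-person correlation. Under assumed losses of 5% to 10% of sessions, the first leaves about 6 to 9 of 10 patients per arm. Under assumed correlations of 0.3 to 0.7, the second gives a false-positive rate of about 15% to 27% for the group effect. All these rates are assumptions.

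Bias in sham versus active is possible but not shown. It needs missingness related to recovery or tolerability; if sessions are lost completely at random, only precision suffers.

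The point is confined to EVestG. A reader might extend it to RPQ, MoCA, MADRS and Stroop, but the plan names MANOVA only for the EVestG features. For the clinical scores, Objective 3 promises only unspecified statistical analysis.

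This should be changed before analysis. It is more than a missing detail, because a named method would be replaced by one that suits the design better.

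**What to change.** In Data analysis, replace the across-session MANOVA with a linear mixed model for each EVestG feature:

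- Fixed effects: group, session and group-by-session.
- Within-person correlation: an unstructured covariance where it can be estimated, otherwise a participant random effect (which assumes equal correlation between sessions).
- Small-sample degrees of freedom, such as Kenward-Roger.
- Data: every recorded session of every randomised patient in the assigned group, plus the controls.
- Reporting: the number contributing at each session, by arm.

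Name a short list of features for the treatment comparison beforehand, and label the remaining feature search exploratory. This keeps the feature discovery in Objective 5 while separating it from the treatment test. Using the same model for the clinical scores is optional.

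**Cost.** Plan wording and some extra analysis work, with no new data. There will be one model per feature instead of one joint test, which is why the list must be short. The model's validity still requires that missingness depends only on data already observed.

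### The EVestG MANOVA does not say how each person's four recordings are handled; if they are entered as separate rows, group tests reject falsely about 15% to 44% of the time (assumed correlation 0.3 to 0.9)

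*Combined protocol and SAP*

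**What the plan says.** The only group-comparison test named is in Data analysis, under Statistical Analysis, Clustering, Decision Making and Validation: "the multivariate Analysis of Variance (MANOVA) statistical test will be run to determine the significant differences". The responses are the EVestG biofeatures. Sessions and groups appear together in one phrase as the things compared: "significant differences of any of the extracted biofeature measures between the sessions and the Control Group and the Treatment and Sham Groups". The threshold is common to all tests: "In all instances, a p-value less than 0.05 is considered significant".

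The EVestG Measurement section makes the data repeated: "All study participants (in all three groups) will go through four sessions of EVestG assessments". Table 1 places the recordings at weeks 0, 4, 8 and 12.

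The documents do not mention a subject effect, a repeated-measures form, a covariance structure or a unit of analysis. They do not say that the four recordings of one person are treated as independent either. No treatment-by-session test is named. Objective 8 plans to "investigate the consistency of the EVestG data between the sessions" in healthy controls, so the protocol itself asks how alike one person's recordings are. The analysis text does not take this up.

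**The concern.** Recordings from the same person are likely to be correlated. A test between groups must be judged against variation between people, and a test of change must be judged against variation within people. If the recordings enter the MANOVA as separate rows, both are judged against one pooled error, and the two mistakes run in opposite directions. Group tests reject too often, while session and group-by-session tests reject too rarely.

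Both matter here. Features found significant among the groups go on to the discriminant analysis, so false group positives carry into the claim that EVestG identifies concussion. Theme 2 looks for features that change because of rTMS. That is a treatment-by-session question, and it is the one this layout is least able to answer.

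**Working it through.** **Inputs from the documents**
- Patients: "A total of 20 individuals with a clear diagnosis of TBI within the last 12 months". Allocation: "Ten patients will be randomly assigned to" Treatment and 10 to Sham. Controls: "20 age-and-gender-matched cognitively healthy volunteers will be recruited as controls for the EVestG assessment". Total 10 + 10 + 20 = 40 people.
- Four recordings each: 40 × 4 = 160 recordings, of which 20 × 4 = 80 are from patients.
- Alpha 0.05.

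**Assumptions, not in the documents:** complete data, normal features, total variance 1, and the same correlation ρ between any two sessions of one person, with ρ from 0.1 to 0.9. The plan gives no power, SD or effect size, so there is no figure of its own to reproduce.

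**Step 1: error degrees of freedom.** With rows as units and 3 × 4 = 12 cells: 160 − 12 = 148. For Treatment v Sham with 2 × 4 = 8 cells: 80 − 8 = 72. With people as units: 40 − 3 = 37 and 20 − 2 = 18.

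**Step 2: why the group test is inflated.** With no true difference, the group mean square has expectation 1 + 3ρ. The pooled residual mixes 37 between-person df with expectation 1 + 3ρ and 111 within-person df with expectation 1 − ρ:

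[37(1 + 3ρ) + 111(1 − ρ)] / 148 = 148 / 148 = 1.

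The F ratio is therefore too large by about 1 + 3ρ. For three groups the 5% critical value of F(2,148) is 3.06, and P(F > x) = (1 + 2x/148)^(−74). At ρ = 0.5, x = 3.06 / 2.5 = 1.22, which gives about 0.30. At ρ = 0.3, x = 3.06 / 1.9 = 1.61, giving 0.20. At ρ = 0.9, x = 3.06 / 3.7 = 0.83, giving 0.44.

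**Step 3: simulated false-positive rates, one feature, recordings as rows (20,000 runs)**

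| ρ | Three groups | Treatment v Sham |
|---|---|---|
| 0.1 | 0.10 | 0.09 |
| 0.3 | 0.20 | 0.15 |
| 0.5 | 0.30 | 0.21 |
| 0.7 | 0.38 | 0.27 |
| 0.9 | 0.44 | 0.31 |

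At ρ = 0 the rate is about 0.05, as it should be. With the person as the unit it stays between 0.046 and 0.054 for every ρ. With several independent features tested jointly (Wilks, three groups, ρ = 0.5), the row-level rate is 0.53 for three features and 0.69 for five.

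**Step 4: why within-person tests are too conservative.** Session and group-by-session mean squares have expectation 1 − ρ under the null, but they are divided by a residual with expectation 1. For Treatment v Sham, the simulated size of these tests at ρ = 0.5 is 0.002 to 0.003 instead of 0.05.

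**Step 5: power for Treatment v Sham by session.** Take a 0.8 SD shift in Treatment at the three post-baseline sessions. The session differences (0, 0.8, 0.8, 0.8) have mean 0.6, so the squared deviations sum to 0.36 + 3 × 0.04 = 0.48. The noncentrality is (10 × 10 / 20) × 0.48 / (1 − ρ) = 2.4 / (1 − ρ), that is 4.8 at ρ = 0.5 and 8.0 at ρ = 0.7. Against F(3,54) this gives power of about 0.40 and 0.62. Simulated:

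| Shift, ρ | Rows as units | Person as unit |
|---|---|---|
| 0.5 SD, 0.5 | 0.02 | 0.17 |
| 0.8 SD, 0.5 | 0.09 | 0.39 |
| 0.8 SD, 0.7 | 0.04 | 0.62 |
| 1.0 SD, 0.3 | 0.25 | 0.44 |

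**Step 6: power for the session main effect (ρ = 0.5).** Rows v person: 0.18 v 0.60 for a 0.5 SD shift in the 20 patients, 0.71 v 0.96 for 0.8 SD in the 20 patients, and 0.99 v 1.00 for 0.8 SD shared by all 40 people.

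**The case against.** The strongest reply is that the plan is silent rather than wrong. MANOVA is also a standard repeated-measures method, with one person's sessions as the response vector, and that form holds the group test at 5%. This stands: a reader might infer that the plan treats the recordings as independent, but no sentence says so. However, the silence leaves the invalid layout open. The valid layout also needs decisions that the plan does not make. With four sessions per feature, 37 error df carry at most 9 features (37 / 4 = 9.25), and 18 carry at most 4 (18 / 4 = 4.5). The three example features (fractal dimension, kurtosis, skewness), if taken for each of the seven stimuli, already make 3 × 7 = 21.

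Three other strong readings also go too far.
- One might quote a 3-fold to 9-fold inflation as a fact. It runs from 0.15 / 0.05 for Treatment v Sham at ρ = 0.3 to 0.44 / 0.05 for three groups at ρ = 0.9. Treatment v Sham alone reaches about 6-fold, at ρ = 0.1 the excess is about 2-fold, and every value depends on an assumed correlation.
- One might say that all within-person tests lose most of their power. This holds for the 0.8 SD interaction at ρ of 0.5 or more. It does not hold for the session main effect when shifts are large or shared, nor for a 1.0 SD interaction at ρ = 0.3.
- One might describe the MANOVA null as exchangeability of all recordings. The null is equal mean vectors; independence of rows is an assumption behind the test.

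The study calls itself a pilot, and the MANOVA sentence concerns EVestG features, so this calculation does not address the symptom scales of Theme 1. That limits the scope of the point. But the Proposal Summary gives EVestG a role in judging treatment efficacy, and significant features go forward to classification.

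**Conclusion.** The concern holds as a conditional one. The plan compares sessions and groups in one MANOVA without stating the unit of analysis or a within-person error. If it is carried out with recordings as rows, and if the between-session correlation is 0.3 to 0.9, a one-feature group test at nominal 5% rejects falsely about 20% to 44% of the time for three groups and 15% to 31% for Treatment v Sham. At correlation 0.1 the rates are about 9% to 10%. The Treatment v Sham by session test, which the plan does not name but Theme 2 needs, would have about 9% instead of 40% power at correlation 0.5 and 4% instead of 62% at 0.7, for a 0.8 SD shift. The figures rest on equal correlation between sessions, normal features and complete data. The direction of both errors follows from any positive correlation of this form; the size depends on a value that the documents do not give. Because this is the only group-comparison test named, it should be settled before analysis.

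**What to change.** In Data analysis, state that the person is the unit of analysis and that the four recordings of one person are never entered as independent rows. Then specify one of two methods:
- For each of a small set of biofeatures chosen in advance, a mixed model with group, session, group-by-session and a person effect, with small-sample degrees of freedom (for example Kenward-Roger). A random intercept assumes equal correlation across weeks 0, 4, 8 and 12, so include a check of that assumption.
- A repeated-measures MANOVA limited to the number of features that the error df can carry (at most 9 for the three groups, 4 for Treatment v Sham).

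Name the Treatment v Sham by session contrast as the test of rTMS effect on EVestG. Control multiplicity across the features: three independent true-null features each tested at 0.05 give 1 − 0.95³ = 14% for at least one false positive.

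The cost is plan wording and a standard model fit, with no new participants or recordings. The downside is that group p-values will be less favourable than a row-level MANOVA would report, and fewer features can be tested.

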### **Standard Neuropsychological and Screening Measures**

The neuropsychological assessments include: Rivermead Post Concussion Symptoms Questionnaire (RPQ) [7,59], Montreal Cognitive Assessment (MoCA) [60], Montgomery Asberg Depression Rating Scale (MADRS) [61] and Stroop tasks [62]. Patients with TBI will go through all above mentioned assessments four times, similar to EVestG assessments. The healthy Control Group will go through only MoCA and MADRS assessments at the beginning of the study and at the last assessment session.

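### No baseline adjustment is specified for Treatment v Sham, although every patient has a week-0 value; at 10 v 10 this can cost much precision, whichever effect the planned MANOVA is meant to test

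*Combined protocol and SAP*

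**What the plan says.** Under Data analysis, "the multivariate Analysis of Variance (MANOVA) statistical test will be run to determine the significant differences of any of the extracted biofeature measures", and the differences sought are those "between the sessions and the Control Group and the Treatment and Sham Groups". The threshold is common to all tests: "In all instances, a p-value less than 0.05 is considered significant".

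EVestG Measurement sets out four sessions, of which the first three are "1) before rTMS treatment, 2) after 12 sessions of rTMS treatment, 3) four weeks after the last rTMS treatment"; the fourth follows at eight weeks. Table 1 places them at weeks 0, 4, 8 and 12 and labels week 0 as baseline, with no treatment yet given. The clinical and neuropsychological scales follow the same timetable: "Patients with TBI will go through all above mentioned assessments four times, similar to EVestG assessments".

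On numbers, "Ten patients will be randomly assigned to Treatment Group and 10 others to Sham Group", and "20 age-and-gender-matched cognitively healthy volunteers will be recruited as controls for the EVestG assessment".

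The plan names no covariate, change score, interaction term or Treatment v Sham contrast. The MANOVA sentence concerns EVestG features only. For RPQ, MoCA, MADRS and Stroop, Theme 1 of the Objectives promises a statistical analysis without naming a model. The trial is described as a pilot and gives no power calculation.

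**The concern.** Week 0 is measured before any stimulation, so randomisation makes the two arms equal in expectation there. It carries no information on the treatment effect by itself, but it does predict each patient's later values. In a trial with 20 randomised patients it is a source of precision that costs nothing further to collect. Without adjustment, chance differences at baseline also remain in any comparison of post-treatment values. With 10 per arm, the difference between arm means at week 0 has standard deviation sqrt(2/10) = 0.45 SD.

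The result matters beyond the pilot's own report. Research Plan and Methods makes the later offer of active treatment to the Sham Group depend on the treatment being shown to work, and the plan tests at 0.05. Naming the adjustment in advance also prevents a choice among raw, change and adjusted analyses once the data are seen.

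**Working it through.** The documents state no power, effect size, SD or correlation, so there is no figure of the plan's to reproduce.

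**Inputs from the documents.** 10 v 10 (Study Population/Participants); four sessions, the first before treatment (EVestG Measurement, Table 1); significance level 0.05 (Data analysis).

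**Assumptions, not in the documents.** Two-sided tests; one normally distributed outcome with SD 1; constant effect d = 0.8 at weeks 4, 8 and 12 and zero at week 0; equal correlation r between any two sessions, with r = 0.4, 0.6, 0.8; no dropout.

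**Per-patient variance of each summary**

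- Mean of all four sessions: (1 + 3r)/4 = 0.55 / 0.70 / 0.85. Its effect is (0 + 0.8 + 0.8 + 0.8)/4 = 0.6, which is three quarters of d.
- Mean of the three post-treatment sessions, unadjusted: (1 + 2r)/3 = 0.60 / 0.733 / 0.867, effect 0.8.
- Post-treatment mean minus week 0: (1 + 2r)/3 + 1 − 2r = 0.80 / 0.533 / 0.267, effect 0.8.
- Post-treatment mean adjusted for week 0: (1 + 2r)/3 − r² = 0.44 / 0.373 / 0.227, effect 0.8.

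**Signal-to-noise ratio**, effect / sqrt(2 × variance / 10):

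- Four-session mean: 1.81 / 1.60 / 1.46
- Change: 2.00 / 2.45 / 3.46
- Adjusted: 2.70 / 2.93 / 3.76

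**Group-by-session, multivariate.** The noncentrality is (10/2) × d² × 0.75/(1 − r) = 2.4/(1 − r) = 4 / 6 / 12, referred to F on 3 and 16 df. These are the squares of the ratios for change (2.00² = 4, 2.45² = 6, 3.46² = 12). Under these assumptions the interaction test therefore carries the same signal as the change score, and it falls below change only because it spreads that signal over 3 df. Change in turn falls below the adjusted analysis because it subtracts the whole baseline value with its noise.

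**Power**

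| Analysis | r = 0.4 | r = 0.6 | r = 0.8 |
|---|---|---|---|
| Group effect over four sessions | 40% | 33% | 28% |
| Group-by-session, multivariate, 3 df | 29% | 42% | 73% |
| Group-by-session, univariate, 3 df | 33% | 48% | 81% |
| Post-treatment mean, unadjusted | 59% | 51% | 44% |
| Change from week 0 | 47% | 64% | 91% |
| Week 0 as covariate | 70% | 76% | 93% |

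The univariate interaction and covariate rows are simulated; the covariate row thus includes the cost of estimating the slope and of chance baseline imbalance. The other rows are exact, and simulation agrees to about one point. With no true effect, rejection rates were close to 5% for every analysis.

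**Sensitivity, d = 1.0 unless stated**

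- r = 0.3: interaction tests 38% to 44%, covariate 87%.
- r = 0.8: interaction tests 91% to 95%, covariate 99%.
- First-order autoregressive correlation, r = 0.7: interaction tests 58% to 63%, covariate 83%.
- Effect fading as 1, 0.75, 0.5, with r = 0.5: interaction tests 38% to 45%, covariate 66%.

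**The case against.** The strongest reply is that the plan does not say what the criticism needs it to say. It does not state that group is averaged over four sessions, nor that a group-by-session term is the test of treatment. That is right. The point therefore cannot rest on one reading, and the size of the loss depends on which is meant. Against the four-session group effect the gap widens as the correlation rises, from 30 points at 0.4 to 65 at 0.8. Against the multivariate interaction it narrows, from 41 points to 20. Against a change score it is only 2 points at 0.8. What stands is that the adjusted analysis came out ahead of each alternative in every setting tried.

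Four stronger readings are tempting, and the documents do not support them:

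- **That week 0 dilutes a group-by-session test.** It does not. In an interaction, week 0 is the reference against which the effect appears. Dilution belongs only to a group effect over all sessions.
- **That week 0 is misused for the clinical scales.** The MANOVA sentence covers EVestG features. For the scales no model is stated, so the defect there is absence.
- **That the planned test is invalid.** Type I error is unaffected in the calculations above.
- **That a stated power is wrong.** None is stated, and the trial is a pilot.

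It is also fair that removing week 0 from the response is not the only sound remedy. A mixed model that keeps it there, with the arms constrained equal at week 0, serves the same purpose.

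**Conclusion.** The point holds as a gap in specification with a cost in precision. The plan collects a week-0 value from every patient, places that session among those to be analysed, and specifies no baseline adjustment for the randomised comparison. At d = 0.8 and correlation 0.6, adjustment raises power to about 76%, from 33% (four-session group effect) or 42% (multivariate group-by-session test). The gain over change from week 0 is 12 points at that correlation.

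These sizes rest on the assumed effect, correlation pattern, complete data and a single outcome. The direction of the gain persisted under autoregressive correlation and a fading effect. The change should be made, but the plan as written is not thereby invalid.

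**What to change.** State in Data analysis that, for each EVestG feature, Treatment and Sham are compared on the values at weeks 4, 8 and 12 with that feature's own week-0 value as covariate. An equivalent is a mixed model with all four sessions in the response and the arms constrained equal at week 0. Say which term or contrast is the treatment effect. Run this comparison on the 20 randomised patients alone; the comparison with the healthy controls is not randomised and belongs in a separate analysis.

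Name the same model for RPQ, MoCA, MADRS and Stroop, each with its own week-0 score, since the plan gives none.

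The cost is analysis wording and one degree of freedom (17 instead of 18 for a single comparison of post-treatment means). No additional patients, visits or measurements are needed.
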